STUDY PROTOCOL

Study name	Understanding Non-Response in Spine Fusion Surgery
Principal investigator	[name], MPH
Project lead	[name], MPH
Document Date	2/6/2019

CONTENTS

Study protocol	1
Abstract.....	2
Objective	2
Design.....	2
Recruitment Workflow Notes	2
Original Recruitment Design	3
Data Collection Design	4
Methods.....	4
Likely impact	5

ABSTRACT

There is considerable debate about the effectiveness of spine fusion surgery for degenerative disc disease (DDD) and other diagnoses related to chronic back pain. As many as 1-in-3 patients who undergo spine fusion do not report improvements in pain or functional status. Additionally, there are currently no evidence-based selection criteria to help surgeons determine which patients will respond to spine fusion surgery and which will not benefit.

The goal of this study was to better understand which patients are more likely to benefit from spinal fusion surgery. The Comparative Effectiveness Research Translation Network (CERTAIN) Spine Fusion Study partnered with spine surgery clinics to invite patients to participate in research activities designed to identify the impact of spine fusion surgery on the outcomes that matter most to patients. As part of this study, patients took surveys before and after their spine fusion surgery, and shared elements of their medical records for review. CERTAIN anticipated that this study would produce a paradigm that clinicians can use with patients to determine whether spine fusion surgery is right for them and identify any modifiable risk factors that may impact their response to surgery.

OBJECTIVE

Determine patient characteristics associated with non-response among patients undergoing lumbar fusion for DDD.

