This exploratory study is being conducted because the prevalence of these characteristics needs to be determined in order to develop accurate predictive algorithms and risk factors for non-response to lumbar spine fusion surgery. Additionally, the findings of this study will be used to establish a statistical and methodological framework to identify patients at high-risk for non-response, informing both decision makers and future interventions aimed at modifiable factors.

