STATISTICAL ANALYSIS PLAN

Study name	Understanding Non-Response in Spine Fusion Surgery
Principal investigators	[name], MPH
Project lead	[name], MPH
Document Date	2/6/2019
Team conducting analysis	[name], MS [name], MPH
Version	3

AIM 1

We will assess baseline covariates with respect to the primary outcome, the Oswestry Disability Index (ODI) failure to achieve at least a 15% improvement (minimal important clinical difference as established by the Food and Drug Administration [FDA]) in the ODI score which ranges from 0 to 100 where 0 indicates not disability and 100 indicates complete disability when comparing baseline to six months after surgical procedure, reporting proportions for categorical variables and means and other measures of central tendency for continuous variables. We will use a multivariate logistic regression model with robust standard errors to evaluate these covariates and the primary outcome. A latent class analysis will be used to identify clusters of traits (e.g., patients with depression, anxiety, and catastrophizing) that tend to be grouped together within patient subtypes. This technique assumes there are distinct patterns and that individuals can be grouped into a small number of clusters representing each outcome path (the “latent classes”). The association between clusters and non-response will be described using logistic regression models accounting for repeated testing. As a sensitivity analysis, we will repeat the latent class analysis on the raw percentage change of the primary outcome measure to examine the robustness of variables that define latent classes. We will also conduct a sensitivity analysis looking for different degrees of change in the primary outcome beyond the 15% threshold defined by the FDA. We will also conduct a missing data analysis to describe and characterize enrolled participants who do not provide further outcome measures due to attrition. We will conduct sensitivity analyses using 10-fold multiple imputation to assess the robustness of the results. We will create an imputation model with variables found to be predictive of missingness and data will be imputed to create 10 complete data sets. The results will then be combined across data sets with the using STATA (i.e., MI) statistical software packages.

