As a sensitivity analysis, we will repeat the latent class analysis on the raw percentage change of the primary outcome measure to examine the robustness of variables that define latent classes. We will also conduct a sensitivity analysis looking for different degrees of change in the primary outcome beyond the 15pts threshold defined by the FDA. We will also conduct a missing data analysis to describe and characterize enrolled participants who do not provide further outcome measures due to attrition. We

will conduct sensitivity analyses using 10-fold multiple imputation to assess the robustness of the results.

We will assess baseline covariates with respect to ODI non-improvement at 60 days, reporting proportions for categorical variables and means and other measures of central tendency for continuous variables. A multivariate logistic regression model with robust standard errors will be used to evaluate these covariates and the primary outcome: ODI non-Improvement at 60 days.

Use a latent class analysis to identify clusters of traits (e.g., patients with depression, anxiety, and catastrophizing) that tend to be grouped together within patient subtypes. This technique assumes there are distinct patterns and that individuals can be grouped into a small number of clusters representing each outcome path (the “latent classes”). The association between clusters and non-response will be described using logistic regression models accounting for repeated testing.

AIM 2

For responders and non-responders, we will perform a descriptive analysis of radiographic characteristics and compare proportions for categorical variables and means for continuous variables. We will explore the associations between radiographic measures and non-response using conditional logistic regression models, as appropriate for matched case-controls studies with multiple controls.

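### The SAP relates latent classes to non-response without handling classification error or excluding ODI from class formation, so the cluster odds ratios are open to bias, typically toward 1 but not always

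*SAP*

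**What the plan says.** The first paragraph of SAP Aim 1 starts the cluster analysis as follows: "A latent class analysis will be used to identify clusters of traits (e.g., patients with depression, anxiety, and catastrophizing", the bracket being examples of traits that may group together. It assumes that "individuals can be grouped into a small number of clusters representing each outcome path". The next step is: "The association between clusters and non-response will be described using logistic regression models accounting for repeated testing". The latent class paragraph that follows the 60-day analysis repeats this plan almost word for word.

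Two other provisions come near the point:

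- a sensitivity analysis in which "we will repeat the latent class analysis on the raw percentage change of the primary outcome measure to examine the robustness of variables that define" the latent classes;
- an imputation exercise, placed directly after the attrition analysis: "We will conduct sensitivity analyses using 10-fold multiple imputation to assess the robustness of the results".

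Neither document states the number of classes or how it is chosen, the indicator variables, an entropy or classification-quality criterion, the rule for assigning patients to classes, or the form in which membership enters the logistic model.

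**The concern.** Class membership is never observed. A latent class model gives each patient a probability of belonging to each class, and placing everyone in the most likely class misplaces some of them. A logistic model fitted to the assigned class takes that label as correct.

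None of the stated safeguards reaches this problem. Adjustment for repeated testing controls multiplicity. The latent class sensitivity analysis asks which variables define the classes, not who belongs to them. The imputation model is built from predictors of missingness and is not said to cover class membership.

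A second gap adds to the first. Describing clusters as standing for outcome paths, and re-running the latent class analysis on percentage change in the outcome, leaves unclear whether ODI helps define the classes. If it does, the later regression on non-response is partly circular.

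At stake is how strongly a psychosocial subtype appears to predict non-response. The protocol's impact section intends the findings to support identification of high-risk patients and work on modifiable factors.

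**Working it through.** The plan gives no odds ratio, sample size or entropy to reproduce, so everything below is illustration. The only input from the documents is a non-response rate of about 1/3, from the protocol abstract ("As many as 1-in-3 patients who undergo spine fusion do not report improvements in pain or functional status"). That rate concerns pain or function generally, not the SAP's ODI criterion, so it serves only as an anchor.

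**1. Two classes, errors unrelated to outcome.** Assumed: share π = 0.3 or 0.5 in the high-risk class, true OR 2 or 3, probability *a* of correct assignment in either class. The class risks p1 and p0 satisfy π·p1 + (1−π)·p0 = 1/3 and odds(p1)/odds(p0) = OR. The risks in the assigned classes are

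- q1 = [π·a·p1 + (1−π)(1−a)·p0] / [π·a + (1−π)(1−a)]
- q0 = [π(1−a)·p1 + (1−π)·a·p0] / [π(1−a) + (1−π)·a]

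Example with π = 0.5 and OR 3: p0 = 0.215, p1 = 0.451. At a = 0.8, q1 = 0.8×0.451 + 0.2×0.215 = 0.4038 and q0 = 0.2×0.451 + 0.8×0.215 = 0.2622. The observed OR is (0.4038/0.5962)/(0.2622/0.7378) = 1.91.

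| Correct assignment | True OR 2 seen as | True OR 3 seen as | Share of log OR kept |
|---|---|---|---|
| 95% | 1.83–1.86 | 2.61–2.67 | 87–90% |
| 90% | 1.69–1.74 | 2.30–2.38 | 76–80% |
| 80% | 1.46–1.51 | 1.82–1.91 | 55–59% |
| 70% | 1.28–1.32 | 1.48–1.53 | 35–40% |

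**2. Three classes.** Assumed: prevalences 0.4, 0.3, 0.3; risks 25%, 25%, 55%; assignment rows (0.9, 0.1, 0), (0.1, 0.8, 0.1), (0, 0.2, 0.8). Everyone assigned to class 1 has risk 0.25. Assigned class 2 has risk (0.04×0.25 + 0.24×0.25 + 0.06×0.55)/0.34 = 0.303. Assigned class 3 has risk (0.03×0.25 + 0.24×0.55)/0.27 = 0.517. Against class 1, the class 3 OR shrinks from 3.67 to 3.21, while the class 2 OR, truly 1.00, becomes 1.30. A noisier matrix, with rows (0.85, 0.1, 0.05), (0.1, 0.7, 0.2), (0.05, 0.2, 0.75), gives 2.52 and 1.26.

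**3. Plain against corrected estimates.** Simulation with two fitted classes, 35% in the high class, baseline risk 28%, true OR 3.0, 200 replicates per setting:

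| Setting | Plain OR, n = 300 / 600 | BCH OR, n = 300 / 600 |
|---|---|---|
| 5 binary traits, entropy about 0.66 | 2.28 / 2.30 | 2.88 / 2.94 |
| 8 binary traits, entropy about 0.79 | 2.54 / 2.59 | 2.91 / 2.96 |

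In the 5-trait setting, plain 95% intervals covered the true OR in 82% of runs at n = 300 and 70% at n = 600. A separate simulation, also with true OR 3.0, gave 70–79% at entropy about 0.65 and 89–95% at 0.79–0.86. At entropy 0.90 there is little bias: plain ORs were 2.82 to 2.95.

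**4. Outcome used as a class indicator.** Simulation with 5 binary traits, class prevalence 0.4, true OR 2.5, 150 replicates at N = 300 and 40 at N = 2000. With weak indicators at N = 300 (82% correct), the median OR was 2.95 with the outcome in the class model and 1.82 without it; the BCH-type correction gave 2.35. In the other three settings the outcome-in-model OR was 2.05 to 2.35.

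**The case against.** The strongest reply is that the SAP does not commit to a faulty method. A reader might infer that membership will be treated as known. The text says only that logistic models will be used, which also fits posterior-weighted, bias-corrected or joint models. That stands: this is an omission. Assign-then-regress is still the natural reading, and an analyst could follow the SAP to the letter and report materially different odds ratios depending on the choice made.

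A reader might also infer that the odds ratios must shrink toward 1. That needs two classes and errors unrelated to outcome. The SAP allows a small number of clusters, not specifically two, and does not rule ODI out of class formation. Steps 2 and 4 show movement the other way.

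The size is also open to challenge. The protocol rationale lists about ten constructs with standardized measures. With 10 binary indicators, the step 3 prevalence, risk and OR, and item probabilities of 0.7–0.8 against 0.2–0.3, the observed OR is 2.47–2.90, mostly about 2.7, at 92–98% correct assignment. That calculation treats the class model as known, so it is somewhat optimistic, but it shows that the loss may be modest.

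Nor do the documents support ranking the cluster odds ratio as a main result. The SAP names a covariate logistic model for the primary outcome and says the cluster association will be described. The protocol calls the work exploratory ("This exploratory study is being conducted because the prevalence of these characteristics needs to be determined").

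**Conclusion.** The concern holds as an omission with a predictable consequence. The SAP specifies no handling of classification error and does not exclude ODI from class formation. Under assign-then-regress with two classes formed without the outcome, the loss ranges from about a tenth of the log odds ratio at 95% correct assignment to over 40% at 80%. These figures rest on assumed prevalence, odds ratio and accuracy, and the documents cannot narrow them.

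Direction is not guaranteed, so a reader of the results could not simply discount the odds ratio upward. Plain intervals can under-cover, and in the 5-trait simulation coverage was worse with more patients. That reflects at least in part an interval centred on a biased value. The calculations do not show that the intervals are too narrow in themselves.

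The BCH estimates lay closer to the truth than the plain ones when classes were poorly separated, though not exactly on it (2.35 against 2.5 with weak indicators). The gain is slight when separation is good. The effect is on interpretation of the cluster odds ratios. A change is worth making, but no confirmatory conclusion depends on it.

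**What to change.** In both latent class paragraphs of SAP Aim 1:

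- State that classes are formed from baseline traits only, without ODI or change in ODI. Name the indicators and the rule for choosing the number of classes, since the correction cannot be specified without them.
- State that the association with non-response is estimated by a bias-adjusted three-step method (BCH or ML) using the estimated classification-error matrix.
- Report entropy and the classification table. Show the plain assigned-class odds ratio only for comparison.
- Say what the repeat analysis on percentage change in the outcome is for, and keep it separate from the classes used in the association model.

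The cost is a few sentences and some extra code, including aligning class labels across the 10 imputed data sets before pooling. Confidence intervals will be wider. No new data are needed.

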- Tablets: Original grant depended on patients completing CERTAIN baseline for themselves via tablet in clinic waiting room, however, patients and staff had technical difficulty with tablets
- Time: not enough time in waiting room or during rooming process to complete the CERTAIN baseline, let alone SF screening and recruitment
- Variability: each CERTAIN clinical site implemented CERTAIN at a slightly different point in their workflow (i.e. in waiting room, after rooming, after surgery scheduling, etc.) which made it difficult to provide clinic staff with guidance about how to assist with enrollment
- QI vs. Research: by not classifying SF as a multi-site study with "engaged" sites, the flexibility to allow clinic staff to actively enroll patients was lost (the exception to this is Evergreen, who had separate IRB approval for a research-only approach to enrollment, not QI)

Data Collection Design

A combination of Quality Improvement (QI) databases and research databases were used to complete the final dataset for this study. Most hospitals in Washington (WA) State participate in a novel, prospective care surveillance initiative called Spine Surgical Care and Outcomes Assessment Program (Spine SCOAP) that allows benchmarking on the indications for, processes of care, clinical outcomes and changes in patient reported outcomes (PROs) including pain and function for patients undergoing spine surgery. Spine SCOAP's analytic group, the Comparative Effectiveness Research Translation Network (CERTAIN) assesses PROs at 60-90 days, 12 and 24 months. Spine SCOAP data was obtained through CERTAIN, and research data was collected directly from patients via email or mail, rather than in the clinic as originally proposed. These surveys included additional baseline, 60-day, and 1-year characteristics and the outcome measures to the original CERTAIN surveys through the DatStat platform.

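### The only planned re-analysis for drop-out is multiple imputation that in effect assumes missing at random, so it cannot show robustness to loss that depends on the unseen outcome

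*SAP*

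**What the plan says.** The primary analysis in SAP Aim 1 estimates covariate associations: "We will use a multivariate logistic regression model with robust standard errors to evaluate these covariates and the primary outcome". The outcome is failure to improve on the ODI "when comparing baseline to six months after surgical procedure". A later paragraph of Aim 1 instead gives the primary-outcome label to ODI non-improvement at 60 days.

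Aim 1 plans two things for drop-out:

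- A description: "We will also conduct a missing data analysis to describe and characterize enrolled participants who do not provide further outcome measures due to attrition".
- A re-analysis: "We will conduct sensitivity analyses using 10-fold multiple imputation to assess the robustness of the results". This is repeated further on in Aim 1.

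On method, the SAP says "We will create an imputation model with variables found to be predictive of missingness" and "The results will then be combined across data sets with the using STATA (i.e., MI) statistical software packages". It names no missingness assumption. It does not say whether the analysis covariates or another ODI measurement enter the imputation model, and it describes no departure from standard imputation. The other sensitivity analyses (raw percentage change, other thresholds) do not concern missing data.

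The Protocol (Recruitment Workflow Notes) makes return of the baseline survey a condition of enrolment. Under Data Collection Design, "research data was collected directly from patients via email or mail, rather than in the clinic as originally proposed".

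**The concern.** Because the baseline survey is needed to enrol, missing data should fall mainly on the follow-up outcome. For the research surveys, having an outcome depends on the patient replying after surgery. Replying could plausibly depend on how the patient is doing and on the traits under study, such as depression, catastrophizing or activation.

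The SAP offers imputation as its test of robustness. If mainly the outcome is missing and the imputation uses the same variables as the analysis model, missing outcomes are filled in at the rates seen in comparable completers. The result then has to be close to the complete-case result, whatever the missing patients' true outcomes. A check that agrees almost by construction could be reported as support for associations that selective loss has distorted.

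Two quantities are at stake: the odds ratio for each trait, and the proportion of non-responders. The study is exploratory, but under Likely Impact the Protocol wants prevalences determined and high-risk patients identified.

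**Working it through.** The documents state no drop-out rate, sample size or effect size, so there is no planned figure to reproduce. The inputs below are assumptions, except that about 32% non-response sits near the Protocol Abstract's figure of up to 1 in 3.

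**Step 1. Effect of selective loss on the odds ratio.** For one binary trait, let r(t,y) be the retention probability for trait t and non-response y. Then:

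complete-case OR = true OR × [r(1,1) × r(0,0)] / [r(1,0) × r(0,1)]

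| Retention: trait, non-resp. / no trait, non-resp. / trait, resp. / no trait, resp. | Multiplier | OR seen if truth is 2.0 |
|---|---|---|
| 0.55 / 0.75 / 0.85 / 0.85 | 0.733 | 1.47 |
| 0.65 / 0.75 / 0.85 / 0.85 | 0.867 | 1.73 |
| 0.65 / 0.65 / 0.85 / 0.85 (outcome alone) | 1.00 | 2.00 |
| 0.56 / 0.64 / 0.70 / 0.80 (outcome and trait, multiplicative) | 1.00 | 2.00 |
| 0.75 / 0.55 / 0.85 / 0.85 (first row reversed) | 1.364 | 2.73 |

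The odds ratio is biased only when loss depends on outcome and trait together and not multiplicatively. The bias can go in either direction.

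**Step 2. First row, in 1,000 patients.** Assume 350 patients have the trait. Non-response is 0.27 without it (odds 0.370). Doubling the odds to 0.740 gives 0.425 with it.

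| | All | Followed up |
|---|---|---|
| Trait, non-responder | 148.8 | 148.8 × 0.55 = 81.9 |
| Trait, responder | 201.2 | 201.2 × 0.85 = 171.0 |
| No trait, non-responder | 175.5 | 175.5 × 0.75 = 131.6 |
| No trait, responder | 474.5 | 474.5 × 0.85 = 403.3 |

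- Missing: 1,000 − 787.8 = 212.2 (97.1 with the trait, 115.1 without).
- Complete-case OR: (81.9 × 403.3) / (171.0 × 131.6) = 1.47.
- Observed non-response: (81.9 + 131.6) / 787.8 = 27.1%, against a true 324.3 / 1,000 = 32.4%.

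**Step 3. Missing-at-random imputation.** Each trait group is filled in at its observed rate (32.4% with the trait, 24.6% without). The odds within each group do not change, so the expected OR stays 1.47. Non-response becomes 0.35 × 32.4% + 0.65 × 24.6% = 27.3%. In the missing patients with the trait, the true rate is (148.8 − 81.9) / 97.1 = 69%.

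If follow-up depends on outcome alone (third row of Step 1), the OR is 2.00, but observed non-response is 26.8% against 32.4%.

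**Step 4. Simulation.** With a further covariate and 10 imputations (40 cohorts of 4,000), full-data, complete-case and imputed ORs were 2.03, 1.49 and 1.49 for the first row. They were 2.03, 1.75 and 1.75 for the second, and 2.00, 2.00 and 2.01 for the third. A second simulation (400,000 patients per scenario, trait prevalence 0.30, true OR about 2.0) varied the imputation model:

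| Loss depends on | Complete case | MI, same variables | MI plus 60-day score | MI omitting the trait |
|---|---|---|---|---|
| Trait and covariate only | 1.99 | 1.99 | 1.99 | 1.61 |
| Outcome and trait, additive on the log-odds | 1.78 | 1.78 | 1.84 | 1.51 |
| Mainly outcome-by-trait | 1.30 | 1.29 | 1.46 | 1.21 |
| 60-day score | 1.71 | 1.72 | 1.97 | 1.50 |

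The near-match therefore holds when imputation uses the analysis variables. A 60-day score corrects the OR fully only when loss runs through that score. Omitting the trait pulls the OR toward 1.

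**The case against.** The strongest reply is that several tempting conclusions go further than the documents allow.

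- *A reader might infer that patients doing badly and dropping out is enough to bias the odds ratios.* It is not. Loss on outcome alone leaves the OR at 2.00 and biases only the non-response proportion.
- *A reader might infer that imputation is bound to match the complete-case result.* The SAP's open rule for choosing imputation variables could admit the 60-day or 1-year ODI, and the match then breaks. This stands as a limit. But the SAP does not commit to including them, and in the outcome-by-trait case the 60-day score moved the OR only from 1.30 to 1.46. If 60 days is the primary time point, no earlier post-operative ODI is described.
- *A reader might infer that the attrition analysis leaves out patients who answer at 60 days and then stop.* Its wording can equally mean subsequent measures, which would include them. This is an ambiguity to clear up, not a defect.
- *A reader might infer that every outcome depends on a mailed or emailed reply.* That sentence covers the research data. Spine SCOAP outcomes came through CERTAIN, the Protocol's eligibility criteria mention phone surveys, and the documents do not say which source supplies the ODI.
- *A reader might say the SAP states missing at random.* It does not. That is inferred from the procedure described.

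It is also fair to say that the study is exploratory and that imputation with an attrition description is already more than nothing. However, the description compares only observed data, so it cannot test dependence on unseen outcomes.

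**Conclusion.** The point holds in a limited form. Imputation is the only planned re-analysis for drop-out. As described it assumes missing at random, and without another post-operative ODI it will largely return the complete-case odds ratios. It therefore cannot support a claim of robustness to joint outcome-and-trait loss (odds ratios) or to outcome-dependent loss (non-response proportion).

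Under the assumed 85% / 75% / 55% follow-up, a true OR of 2.0 is seen as about 1.5 by both methods, and non-response of 32% as 27%. With 65% in place of 55%, the OR seen is about 1.75. Other patterns give no bias in the OR or the opposite bias. The retention rates, trait prevalence and effect size are all assumptions. The documents do not show that such loss occurred, only that the planned check could not reveal it. The change is worth making, but the main model need not be replaced.

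**What to change.** Keep the planned imputation and make these additions:

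1. Specify the imputation model: the outcome, all analysis covariates, and any other available post-operative ODI.
2. Add a delta-adjusted version in the same Stata framework. Multiply the imputed odds of non-response by a two-sided grid, for example 1/3, 1/2, 1, 2, 3. Apply it once to all missing patients and once only to those with the trait under test.
3. Report the range of each odds ratio and of the non-response proportion, and the shift at which each main association loses or gains significance.
4. Count as missing every enrolled participant without the primary ODI outcome.
5. Reconcile the six-month and 60-day statements of the primary time point. If six months stands, compare the 60-day ODI of later drop-outs with that of completers to judge which shifts are plausible.

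Expected results for the 1,000 patients above:

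| Multiplier | All missing: OR, non-response | Trait only: OR, non-response |
|---|---|---|
| 1/3 | 1.33, 23.8% | 1.15, 25.5% |
| 1/2 | 1.37, 24.8% | 1.24, 26.1% |
| 1 | 1.47, 27.3% | 1.47, 27.3% |
| 2 | 1.57, 30.6% | 1.80, 28.9% |
| 3 | 1.61, 32.8% | 2.02, 29.9% |

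For example, a trait-only multiplier of 3 gives imputed odds of 3 × 81.9 / 171.0 = 1.44, a probability of 0.589, and 81.9 + 97.1 × 0.589 = 139.1 non-responders of 350. Against 159.9 of 650 without the trait, the OR is (139.1 / 210.9) / (159.9 / 490.1) = 2.02.

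The grid must be two-sided because multipliers above 1 in trait carriers only raise a risk trait's OR, so they could never show where such an association is lost. Both applications are needed because a common shift also moves the OR, though less in this example.

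The cost is a few more runs and some SAP wording, with no new data. The grid is a choice, and some associations may be reported as less robust.

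### The SAP's only stated rule for choosing imputation variables can leave out an analysed trait and pull its odds ratio toward 1 in the multiple-imputation sensitivity analysis

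*SAP*

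**What the plan says.** SAP, AIM 1 models ODI non-response on baseline covariates by logistic regression with robust standard errors, and relates latent classes of traits to non-response by further logistic models. Its examples of such traits are "patients with depression, anxiety, and catastrophizing) that tend to be grouped together within patient subtypes".

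The missing data it describes come from "enrolled participants who do not provide further outcome measures due to attrition". It will "conduct sensitivity analyses using 10-fold multiple imputation to assess the robustness of the results", and the one sentence on content is: "We will create an imputation model with variables found to be predictive of missingness".

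The later paragraphs of AIM 1 repeat the 10-fold imputation without naming any variables. They then set out a regression to "evaluate these covariates and the primary outcome: ODI non-Improvement at 60 days", without saying whether the same imputation rule applies. The protocol refers to the SAP for statistical methods and adds no rule of its own.

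On other ODI measurements, Protocol, Data Collection Design says: "These surveys included additional baseline, 60-day, and 1-year characteristics and the outcome measures to the original CERTAIN surveys". The SAP does not say that these scores enter the imputation model.

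**The concern.** Predicting missingness is a good reason to add an auxiliary variable. It is not a sufficient rule for choosing the whole model. When an outcome is imputed from a model that omits a trait, the imputed values carry no association with that trait beyond what the included variables convey. Mixing them with the observed outcomes dilutes the trait's adjusted odds ratio.

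The study exists to find characteristics associated with non-response, so these odds ratios are its product. The imputation is there to test how robust they are. A sound complete-case association could appear to weaken because of how the imputation variables were chosen, not because of the missing data. The distortion is also selective: traits that happen to predict dropout are kept and the others are shrunk, so comparisons between traits are affected too. By the same reasoning, omitting the latent class inputs would dilute the class associations; this was not simulated.

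**Working it through.** The SAP states no figure to reproduce, so the check is an approximation followed by simulation.

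**Inputs from the documents.** Ten imputations and a logistic analysis model with robust standard errors (SAP, AIM 1). Non-response of about one-third (Protocol, Abstract). Enrolment required a returned baseline survey (Protocol, Recruitment Workflow Notes), so the gap is mainly in the outcome.

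**Assumed.** n = 400, trait prevalence 30%, true odds ratio (OR) 2.0, 5–40% of outcomes missing, and dropout driven by two other covariates in the analysis model.

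**Approximation.** With a fraction f missing, the log OR is about β among observed outcomes and about 0 among imputed ones, so the pooled log OR is about (1 − f)β and the OR about 2^(1 − f).

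**Simulation.** 600 datasets per scenario, combined by Rubin's rules, no 60-day score; Monte Carlo error of the log OR is about 0.01.

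| Missing | 2^(1 − f) | OR, trait omitted | OR, trait included | Power, omitted | Power, included |
|---|---|---|---|---|---|
| 5% | 2^0.95 = 1.93 | 1.92 | 1.99–2.00 | 79% | 83% |
| 10% | 2^0.90 = 1.87 | 1.86 | 1.99–2.00 | 72% | 79% |
| 20% | 2^0.80 = 1.74 | 1.73 | 1.99–2.00 | 56% | 75% |
| 30% | 2^0.70 = 1.62 | 1.62 | 1.99–2.00 | 41% | 66% |
| 40% | 2^0.60 = 1.52 | 1.51 | 1.99–2.00 | 23% | 59% |

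With the trait omitted, 95% interval coverage is 95–97%, falling to 92% at 40% missing.

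**Other settings (trait omitted, no 60-day score).**
- True OR 1.5 at 20%, 30%, 40% missing: 1.37, 1.32, 1.27 (included 1.48–1.49). True OR 2.5: 2.07, 1.89, 1.72 (included 2.51–2.52).
- n = 200, true OR 2.0: 1.79, 1.67, 1.54 (included 2.08–2.09).
- A separate simulation at n = 1000, about 10–40% missing, true OR 2.0: 1.83, 1.69, 1.62, 1.48. Complete-case analysis of the same data gave 1.99–2.07. Coverage with the trait omitted fell to about 61% at 40%. A trait with no effect stayed at 1.01.
- In that simulation, correlation between a continuous trait and an included covariate did not help: 1.46 (correlation 0.3) and 1.45 (0.6) at about 40% missing.

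**With a 60-day score in the imputation model, trait still omitted.** The score is assumed to carry the same trait effect as the later outcome.

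| 60-day score available for | 20% missing | 30% | 40% |
|---|---|---|---|
| All dropouts (residual correlation 0.5–0.85) | 1.85–1.95 | 1.79–1.92 | 1.72–1.90 |
| Half of dropouts (correlation 0.7) | 1.81 | 1.74 | 1.65 |
| No dropouts | 1.73 | 1.62 | 1.50 |

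When the 60-day outcome is itself analysed, no earlier postoperative score exists.

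**Retained covariate correlated with the omitted trait** (true OR 1.5 per SD, correlation 0.5–0.7, trait OR 2.0–2.5): 1.56–1.60, 1.57–1.64 and 1.61–1.69 at 20%, 30% and 40% missing, against 1.52–1.54 with the trait included. This is a small movement away from 1.

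**Check of the proposed remedy** on an assumed ODI scale (baseline mean 48, SD 13), imputing the score and then deriving non-response: OR 2.02–2.03 at 20% and 1.99–2.01 at 40% missing, against 2.04 with full data, with the same results for 15-point and 15% rules. The omitted-trait values on this scale, 1.76–1.77 and 1.53, apply when no dropout has a 60-day score; a further run gave 1.97 and 1.89 when the score was kept.

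**The case against.** The strongest reply is that the SAP does not say *only*. The sentence can be read as naming auxiliary variables to be added to the analysis variables, and experienced analysts may well include those. That reading is possible, and every figure above depends on the narrower one. But the sentence is the only rule the plan gives, and following it literally produces the bias. The reply is a reason to write the intention down.

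The magnitude is also assumed. At 5–10% missing the loss is small (1.92 and 1.86), a well-observed 60-day score reduces it further, and coverage at n = 400 changes little up to 30%. All of this stands. The no-score figures are the upper end, and the documents give no attrition rate that would place the study in the range. The protocol's listed follow-up times also do not include six months, so how closely a 60-day score would track the analysed outcome is uncertain.

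The imputation is a sensitivity analysis, the main regression is untouched, and the protocol describes the work as exploratory ("This exploratory study is being conducted because the prevalence of these characteristics needs to be determined"). That limits the importance of the point without removing it.

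Finally, the remedy below does more than the defect strictly needs: including all analysis variables was enough to recover the odds ratio. Imputing the score rather than the binary outcome is a further choice, made for the reason given there.

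**Conclusion.** The concern holds: as written, the rule gives a wrong result if followed. An analysed trait unrelated to dropout has its log odds ratio shrunk to roughly (1 − fraction missing) of its true value when no other ODI score is used. For a true OR of 2.0 that means about 1.73 at 20% and 1.51 at 40% missing, with power at n = 400 of 56% against 75% and 23% against 59%.

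Direction and approximate size agree between the approximation and simulations with different settings. They rest on the trait being omitted, on dropout depending on other modelled covariates, and on assumed attrition and effect sizes. The main regression is unaffected. The sentence should be amended before the imputation results are used to judge robustness.

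**What to change.** Replace the sentence on the imputation model with:

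> The imputation model will contain the ODI score at the analysed time point, all covariates in the Aim 1 regression models, the trait measures used as latent class inputs, baseline ODI, and ODI scores from other available follow-up times; predictors of missingness will be added as auxiliary variables. Non-response will be derived from the ODI score after imputation, and the binary outcome will not be entered in the imputation model alongside the score that defines it.

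State also that this applies to the 60-day analysis if imputation is used there.

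Imputing the score lets one set of imputations serve the planned sensitivity analysis "looking for different degrees of change in the primary outcome beyond the 15% threshold". The last clause is a safeguard: entering the binary outcome with baseline and six-month ODI gave perfect separation in every dataset checked (50 per scenario).

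The cost is two SAP sentences and a longer command in the same package, with no new data. The downsides are a larger model, possible fitting problems if covariates are many relative to the unstated sample size, and reliance on the model for the score. When a normal model was fitted to a score with logistic errors, the OR was 1.94–1.98 against 1.99–2.00 complete-case. If fitting fails, the minimum to keep is the outcome and every variable in the analysis model.
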